10.2. PROCEDURES

Subjects in the clinical investigation will undergo placement of the ReUnion TSA System. Please see the approved IFU and Operative Technique manuals for a detailed description of the medical device(s) and instrumentation, intended use information and associated risk. Any additional clinically indicated procedures are permitted as deemed necessary by the clinical investigation investigator.

10.3. FOLLOW-UP EVALUATIONS

Subjects in this clinical investigation will be evaluated at Pre-Operative, Operative/Discharge, and at 6 Weeks (4 weeks – 8 weeks), 6 Months (24 weeks – 28 weeks), 12 Months (48 weeks- 56 weeks), 24 Months (100 weeks – 108 weeks) and annually after the index procedure. The follow-up evaluations will include assessment of device-related AEs/incidents, radiographs and ASES Shoulder Score.

Investigative site personnel will contact subjects prior to their scheduled follow-up evaluations to encourage compliance with clinical investigation visits and participation.

If a subject misses a visit and is outside of the visit window, then every effort should be made to collect data instead of noting the visit as missed.

10.4. SCHEDULE OF EVENTS

Assessment	Pre-Operative	Operative/ Discharge	6 Weeks ^{a,b} (+/- 2 weeks)	6 Months ^{a,b} (+/- 3 weeks)	12 Months ^{a,b} (+/- 4 weeks)	24 Months ^{a,b} (+/- 4 weeks)	Annually ^b
Informed Consent	X						
Demographics & Medical History	X						

Inclusion/Exclusion	X						
Physical Exam	X		X ^c				
Surgical Procedure		X					
ASES Shoulder Score	X		X ^d				
Image Evaluation ^{e, f}	X	X	X	X	X	X	X
Subject Disposition ^g			X	X	X	X	X
	Device-Related AEs/Incidents & Reoperations will be collected throughout the course of the clinical investigation.						
	
 a. Follow-up visit schedule to reflect Institutions' Standard of Care practices b. If the subject misses a visit and is outside of the visit window, then every effort should be made to collect data instead of noting visit as missed. c. Evaluation may be collected when subject presents in-clinic for study visit. d. Evaluation can be collected via phone. e. Radiograph collection should follow Institution's Standard of Care practices and no additional x-rays should be made for study purposes. f. CT scans may be collected if part of Institution's Standard of Care practices. g. Subject Disposition assessment will occur at any time point for subject withdrawal prior to the completion of the clinical investigation. 						

Table 1: Schedule of Events

11. Statistical Methods

The 24 months post-operative results for subjects implanted with the ReUnion TSA System will be compared to a historical group and results reported by respective clinical outcome data in the scientific literature. The benchmark sources and values will serve as the control group for the ReUnion TSA System subjects.

Hypotheses are developed to allow for a comparison of 24 months post-operative ASES Shoulder Score results and 24 months effectiveness/performance between these two populations.

The Statistical Analysis Plan (SAP) lists all variables/questions within this clinical investigation. Therefore, no additional “evaluation” chapter is required nor needed for this CIP.

Data will be captured via IBM Clinical Development electronic data capture (EDC) system and statistical analysis will be performed using IBM SPSS. All statistical hypotheses tests will be with confidence levels (1- α) of 95% and power (1- β) of 80%. The significance level (α) is 0.05 and the beta-value (β) is set to 0.20. Therefore, p-values ≤ 0.05 will indicate statistical significance.

Results will be presented using summary tables and optionally supported by graphs. For detailed information per variable, see SAP.

[figure not shown]
The primary endpoint of the clinical investigation is to demonstrate non-inferiority of the device to the selected literature controls, as measured by the ASES Shoulder Score at 24 Months post-operative. Specifically, the proposed study will test the null hypothesis that the population mean is 82.16 points. The criterion for significance (alpha) is set at 0.05. With the sample size of 10 cases, the clinical investigation will have power of 80.3% to yield a statistically significant result. This computation assumes that the population from which the sample will be drawn has a mean of 82.16 points with a standard deviation of 16.76 points. The observed value will be tested against a theoretical value (lower limit - θ) of 65.40 points. To account for an estimated appropriate overall drop-out rate, Stryker intends to enroll the calculated number of subjects, multiplied by the number of cleared indications (5) to reflect the underlying subject population adequately.

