One goal of the proposed clinical investigation is to test the null hypothesis that the population mean is 82.16 points. The criterion for significance (alpha) has been set at 0.05. The test is 2-tailed, which means						

that effects in both directions will be interpreted. With the proposed sample size of 10 cases, the clinical investigation will have power of 80.3% to yield a statistically significant result. This computation assumes that the population from which the sample will be drawn has a mean of 82.16 points with a standard deviation of 16.76 points. The observed value will be tested against a theoretical value (constant, non-inferiority margin) of 65.40 points.

IBM SPSS Sample Power Output – Screenshot

Estimated overall drop-out rate is 56% which leads to the requirement of enrolling additional 6 subjects into the clinical investigation.

Sample Size	Number of subjects to be enrolled: 16 subjects (rounded up to 20 subjects)
Overall Sample Size (multiplied by number of indications (=5))	100 subjects

Table 2: Sample Size Justification

In conclusion, the calculated number of subjects to be enrolled (10) plus the estimated overall drop-out rate of 56% predicts enrollment of 20 subjects per cleared indication (five) to reflect the underlying subject population adequately. As a result, an enrollment target of 100 subjects in total will be aspired.

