11.3.2. Primary Analysis / Endpoint

The objective of the clinical investigation is to demonstrate non-inferiority (equal or better) of the ASES Shoulder Score in relationship to the officially cleared indications in comparison to respective clinical outcome data in the scientific literature.

[figure not shown]
Data collection of ASES Shoulder Score will start pre-operatively and will be collected according to schedule in Table 1. This will be repeated annually in all subjects who have the total or partial prosthesis with full or partial implant survival (including all subjects without removal of all endo-prosthesis components).

The 24 months post-operative results for subjects implanted with ReUnion TSA System will be compared to a historical group and results reported by respective clinical outcome data in the scientific literature. The benchmark sources and values will serve as the control group for the ReUnion TSA System subjects.

Higher ASES Shoulder Score results are linked to better subject results and vice versa.

The clinical investigation endpoint is non-inferiority to the control, meaning the clinical investigation result should be equal or better than the control. In this clinical investigation, an equal or better ASES Shoulder Score result means equal or more (\geq). As only results from samples will be captured, results are mostly estimates of the true population parameter. These estimates vary by a certain area, where it is expected that the true population parameter falls within. Based on this, it is required to specify a lower limit for the acceptable difference or zone of indifference, denoted as $-\theta$.

Hypotheses are developed to allow for a comparison of the 24 months post-operative ASES Shoulder Score effectiveness / performance between the two underlying populations. The 24 months post-operative ASES Shoulder Score is the primary endpoint of this clinical investigation. Hypothesis tests will be one-sided with a significance level α of 5%.

Hypothesis	Equations	Interpretation
Null (H_0)	$A - B < -\theta$	Central tendency of A is inferior to the central tendency of B.
	ReUnion TSA System – Control (Benchmark) $< -\theta$	
Alternative (H_1)	$A - B \geq -\theta$	Central tendency of A is non-inferior to the central tendency of B.
	ReUnion TSA System – Control (Benchmark) $\geq -\theta$	
		
Possible Evidence (p)	Possible Decisions	Possible Conclusions – ASES score

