4.7. CONFIDENCE INTERVALS AND P-VALUES

The following acceptance / rejection criteria were used for this clinical investigation:

Parameter	Acceptance / rejection criteria
Confidence level (1- α)	0.95 (95%)
Significance level (α)	0.05 (5%)
Power (1- β)	0.80 (80%)
Beta-level (β)	0.20 (20%)
Confidence interval of mean	95%
p-value indicating significance	≤ 0.05

Table 4.7: Acceptance / Rejection Criteria

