6.7. ADDITIONAL ANALYSIS

6.7.1. ASES Comparison

The comparison of the ASES Shoulder Score must compare all Total ASES Shoulder Scores of all follow-up visits against each other (m x n) in accordance to table 6.7.1.1 and the analysis tables listed in this chapter. This analysis is part of the final report only.

Comparison		Follow-up Visits (n)											
		Preop	6 Weeks	6 Months	12 Months	24 Months	36 Months	48 Months	60 Months	72 Months	84 Months	96 Months	108 Months
Follow-up Visits B (m)	Preop												
	6 Weeks	x											
	6 Months	x	x										
	12 Months	x	x	x									
	24 Months	x	x	x	x								
	36 Months	x	x	x	x	x							
	48 Months	x	x	x	x	x	x						
	60 Months	x	x	x	x	x	x	x					
	72 Months	x	x	x	x	x	x	x	x				
	84 Months	x	x	x	x	x	x	x	x	x			
	96 Months	x	x	x	x	x	x	x	x	x	x		
	108 Months	x	x	x	x	x	x	x	x	x	x	x	
	120 Months	x	x	x	x	x	x	x	x	x	x	x	x

*All combinations marked with an "x" must be performed

Table 6.7.1.1: All Assessments – ASES Shoulder Score – Follow-up Visits to be compared

Evaluation Variable / Question	Level of Measurement	Analysis Plan
All Assessments – ASES Shoulder Score Comparison		
Use “ASES Total Score m [points]” and “ASES Total Score n [points]”: Based on the underlying distribution of the data in both groups and the result of the normality assessment, either the parametric paired samples t-test or the non-parametric Wilcoxon test will be used to compare “ASES Total Score m [points]” and “ASES Total Score n [points]” to evaluate the ASES Shoulder Score change by subject (improvement or decrease).		
The complete available SPSS tables content related to either the paired samples t-test or the Wilcoxon test will be included in the final report. (Variable(s): FINSCORE)		

Table 6.7.1.2: All Assessments – ASES Shoulder Score Comparison Tables List

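### Protocol section 11 and SAP Table 4.7 attribute 80% power to all hypothesis tests, but only the n=10 primary calculation supports it; the 78 paired ASES visit comparisons were never sized

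*Protocol*

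**What the plan says.** Protocol section 11 (Statistical Methods) states: "All statistical hypotheses tests will be with confidence levels" of 95% and, in the same sentence, with power of 80%. It then gives α = 0.05, β = 0.20 and the rule that p ≤ 0.05 is significant. SAP section 4.7 introduces its table with "The following acceptance / rejection criteria were used for this clinical investigation" and lists power 0.80 and β 0.20 there, tied to no particular test.

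One test is sized, in Protocol 11.1 (Table 2) and SAP 3.2 (Table 3.2): a one-sample comparison of the 24-month ASES mean with 65.40 points. "With the proposed sample size of 10 cases", mean 82.16 and SD 16.76, the stated power is 80.3%. For that calculation "The criterion for significance (alpha) has been set at 0.05" and "The test is 2-tailed, which means" effects in both directions count.

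SAP 6.7.1 adds further hypothesis tests. The analysis "must compare all Total ASES Shoulder Scores of all follow-up visits against each other", by paired t-test or Wilcoxon test, from pre-operative to 120 months, in the final report. It names no target difference, correlation, number of pairs or power. SAP 6.7.4 covers the same visit pairs descriptively, and Table 6.7.4.2 includes the mean change with its 95% confidence interval.

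**The concern.** A significance level can be fixed for every test in a study. Power cannot, because it depends on how many subjects contribute, how variable the measure is and which difference matters. The only difference defined in the plan is the 16.76 points between 82.16 and 65.40, and it belongs to the primary test. Attaching 80% power to every test therefore states a property that the design does not establish.

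The tests affected are the long-range ASES comparisons. Long-term replacement of the joint is among the device's intended purposes, so readers of the final report will look for 24 against 120 months. A non-significant p-value there, beside a protocol statement that all tests have 80% power, can be mistaken for evidence that a decline was excluded. The plan's only written decision rule is p ≤ 0.05; it does not say that the confidence interval governs how these comparisons are interpreted.

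**Working it through.** **1. The plan's own figure.** Inputs from Protocol 11.1: n = 10, difference 82.16 − 65.40 = 16.76, SD 16.76, two-sided α = 0.05. For a one-sample t-test, the noncentrality is √10 × 16.76/16.76 = 3.162 on 9 degrees of freedom. Power from the noncentral t is 80.31%, against 80.3% stated, so it is reproduced.

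The figure belongs to 10 subjects. With the same mean and SD, 44 or 100 subjects give the primary test power above 99.9%. At n = 10 with the one-sided 5% level of Protocol 11.3.2 ("Hypothesis tests will be one-sided with a significance level" of 5%), power would be 89.8%. So 80% describes the sizing calculation, not even the primary test at the planned enrolment.

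**2. How many tests were not sized.** SAP Table 6.7.1.1 has 13 visits (pre-operative, 6 weeks, 6, 12 and 24 months, then yearly to 120 months). Visit pairs: 13 × 12/2 = 78.

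**3. What the design could deliver at 120 months (illustration).**

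From the documents:
- Enrolment 100 and overall drop-out 56%: 100 × (1 − 0.56) = 44 pairs.
- SD 16.76 points.

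Assumed, because the documents do not give them:
- the same SD at both visits;
- within-subject correlation ρ, varied from 0 to 0.8;
- a two-sided 5% paired t-test;
- a 5-point change, used only as an example.

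Formulas: SD of change = 16.76 × √(2(1 − ρ)); noncentrality = (change/SD of change) × √44, with 43 degrees of freedom. At ρ = 0.5 the SD of change is 16.76 and the noncentrality for 5 points is 5/16.76 × 6.633 = 1.98.

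| ρ | SD of change | Power for 5 points | Change detectable with 80% power | 95% CI half-width |
|---|---|---|---|---|
| 0 | 23.70 | 28% | 10.2 | 7.2 |
| 0.3 | 19.83 | 37% | 8.6 | 6.0 |
| 0.5 | 16.76 | 49% | 7.2 | 5.1 |
| 0.7 | 12.98 | 70% | 5.6 | 3.9 |
| 0.8 | 10.60 | 86% | 4.6 | 3.2 |

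**4. Sensitivity.**
- 44 pairs reach 80% power for 5 points once ρ is about 0.76 or more.
- At ρ = 0.5, 80% power for 5 points needs 91 pairs. With all 100 pairs, power is 84% and the detectable change is 4.7 points.
- At ρ = 0.5 and 44 pairs, moving the SD across the plan's own 95% interval for the mean of the source SDs (12.64 to 20.88) takes power for 5 points from 73% to 34%.
- For a 10-point change with 44 pairs, power is 78% at ρ = 0 and 97% at ρ = 0.5.
- For 16.76 points, the one difference that the plan defines, power with 44 pairs is at least 99.6% across this range of ρ.

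Depending on inputs that the plan does not fix, power runs from 28% to nearly 100%. That spread is why no single figure, 80% or any other, can be attached to these tests.

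**The case against.** The strongest reply is that this is one loose sentence. The surrounding text in Protocol section 11 concerns the 24-month hypotheses, so 80% could be read as referring to the primary test alone. The arithmetic of the sized test is right. The visit comparisons are listed as additional analyses for the final report only, and no primary or secondary conclusion depends on them. The estimate and 95% interval for every visit pair are already planned.

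Most of this stands and limits the weight of the point. The narrower reading is hard to hold, however, when the sentence says all tests and SAP Table 4.7 repeats the value for the whole investigation.

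Two stronger readings are tempting, and the documents do not support them.
- **That the late comparisons have about 50% power.** That is one scenario: a 5-point change, ρ = 0.5 and 44 pairs. Neither document sets a 5-point threshold or gives a correlation. The 56% is an overall rate taken from a cited reverse-arthroplasty report with at least 10 years of follow-up, so earlier visits may keep more subjects.
- **That the plan will read a non-significant comparison as no decline.** Nothing in either document says so. SAP 6.7.1 gives the purpose as evaluating change in either direction. Over-reading is a risk that the wording leaves open, not a planned rule.

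**Conclusion.** The point holds as a wrong stated property. The 80% power given to all hypothesis tests in Protocol section 11 and SAP Table 4.7 has a basis only in the 10-subject primary sample-size calculation, and none for the 78 paired comparisons in SAP 6.7.1. This conclusion needs no outside assumption.

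The size is illustrative. With 44 pairs, SD 16.76 at each visit and two-sided 5%, the change detectable with 80% power is about 7.2 points at ρ = 0.5 (10.2 at ρ = 0, 4.6 at ρ = 0.8), and power for an assumed 5-point change is 28% to 86% over the same range of ρ. These figures are for the paired t-test; the Wilcoxon alternative was not evaluated. It is not established that the comparisons are underpowered for a difference that matters, because the plan names no such difference for them.

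**What to change.** 1. In Protocol section 11 and SAP Table 4.7, keep the 5% level as the general criterion and tie the 80% to the primary sample-size calculation with 10 subjects. Attaching it to the primary test at the planned enrolment would still be inaccurate (working, step 1).
2. In SAP 6.7.1, state that the visit comparisons were not sized and are descriptive. If a detectable change is quoted, give its assumed SD, correlation and number of pairs in the same sentence, preferably over a range of correlations.
3. State in SAP 6.7.1 or 6.7.4 that maintenance of function is judged from the 95% confidence interval of within-subject change in Table 6.7.4.2, and that p > 0.05 is not evidence of no decline.

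The cost is a few sentences in two documents and a less favourable stated property for additional analyses. No new subjects, data or analyses are needed.

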11.1. DETERMINATION OF SAMPLE SIZE

For details of the sample size determination, see Table 2.

[figure not shown]
Benchmark and Objectives for Clinical Investigation																															
Endpoint		Non-inferiority (equal or better) of the ASES Score in relationship to the officially cleared indications in comparison to respective clinical outcome data in the scientific literature.																													
Estimated drop-out rate		56% (confirmed by Medical Expert, see Cuff et al. [1])																													
Benchmark Sources & Values ASES [points]																															
Source		n	Mean	Std. Dev.	Comments No.																										
No.	Title																														
1	Irlenbusch et al. [2]	73	77.9	N/A	Conflict related to Follow-Up times in abstract vs method vs result section.																										
2	Flurin et al. [3]	73	90.3	14.6	Not clear if SD or 95% CI																										
3	Press et al. [4]	34	82.6	19.4																											
4	Hsu et al. [5]	25	94.4	N/A																											
5	Kiet et al. [6]	40	80	21	N changed from 45 to 40																										
6	Steen et al. [7]	96	80.4	22.4	Not clear if SD or 95% CI																										
7	Gulotta et al. [8]	40	80.1	10.1																											
8	Petri et al. [9]	43	83.5	13.1																											
9	Schoch et al. [10]	78	88.4	16.7																											
10	Alentorn-Geli et al. [11]	38	64	N/A	TSA und HA combined.																										
Identified Cleared Indications																															
No.	Indication																														
1	Post-traumatic arthritis																														
2	Degenerative arthritis																														
3	Rheumatoid arthritis																														
4	Revision of previous unsuccessful total shoulder replacement, resurfacing or other procedure																														
5	Aseptic necrosis																														
Explorative Meta-Analysis - ASES (single group)																															
Acceptance Criteria																															
Confidence Interval (CI)					0.95 (95%) two-sided																										
Software Used					IBM SPSS V20																										
Case Processing Summary																															
	
  
 	Cases	
 
 	Valid	Missing	
 
 	N	Percent	N	
   
 		
 
 		
 
 		
  
						Cases					Valid		Missing			N	Percent	N												
		Cases																													
		Valid		Missing																											
		N	Percent	N																											
				Total																											
		N	Percent	N																											
Mean ASES ReUnion_TSA_CER		10	100,0%	0	0,0%																										
Std.Dev. ASES ReUnion_TSA_CER		7	70,0%	3	30,0%																										
					10																										
					100,0%																										

 | | | |

Descriptives						
			Statistic			
Std.Dev. ASES ReUnion_TSA_CER			16,7571			
Mean 95% Confidence Interval for Mean			Lower Bound 12,6353 Upper Bound 20,8790			
Median Std. Deviation Minimum Maximum Interquartile Range			16,7000 4,45678 10,10 22,40 7,90			
Mean ASES ReUnion_TSA_CER			82,1600			
95% Confidence Interval for Mean			Lower Bound 76,2372 Upper Bound 88,0828			
Median Std. Deviation Minimum Maximum Interquartile Range			81,5000 8,27945 64,00 94,40 9,40			
						
Red line: Pooled mean ASES Blue lines: 95% CI of pooled mean ASES Black line: Pooled median pooled ASES Box: Interquartile Range Green Line: Pooled mean ASES minus pooled std. dev. ASES (16.76) $82.16 - 16.76 = \mathbf{65.40 \text{ points}}$						
Acceptance Criteria for Sample Size Calculation						
Significance Level (α)	0.05 (5%)					
Power (1-β)	0.80 (80%)					
Confidence Interval (CI)	0.95 (95%)					
Tails	2					
Path	Non-inferiority – ReUnion TSA (A) \geq Benchmark (B, explorative meta-analysis in this document)					
Hypotheses Pair	Null (H_0)		A – B $< -\theta$			
	Alternative (H_1)		A – B $\geq -\theta$			
Benchmark Timepoint	24 months post-operative					
Benchmark n (sources)	10					
Benchmark Mean	82.16 (pooled mean ASES [points])					
Benchmark Std. Dev.	16.76 (pooled std. dev. ASES [points])					
Benchmark Value	Pooled mean ASES minus pooled std. dev. ASES (16.76)					
Non-Inferiority Margin (-θ)	$82.16 - 16.76 = \mathbf{65.40 \text{ points}}$					
Software Used	IBM SPSS Sample Power V3.0					
IBM SPSS Sample Power Output						
One goal of the proposed clinical investigation is to test the null hypothesis that the population mean is 82.16 points. The criterion for significance (alpha) has been set at 0.05. The test is 2-tailed, which means						

that effects in both directions will be interpreted. With the proposed sample size of 10 cases, the clinical investigation will have power of 80.3% to yield a statistically significant result. This computation assumes that the population from which the sample will be drawn has a mean of 82.16 points with a standard deviation of 16.76 points. The observed value will be tested against a theoretical value (constant, non-inferiority margin) of 65.40 points.

IBM SPSS Sample Power Output – Screenshot

Estimated overall drop-out rate is 56% which leads to the requirement of enrolling additional 6 subjects into the clinical investigation.

Sample Size	Number of subjects to be enrolled: 16 subjects (rounded up to 20 subjects)
Overall Sample Size (multiplied by number of indications (=5))	100 subjects

Table 2: Sample Size Justification

In conclusion, the calculated number of subjects to be enrolled (10) plus the estimated overall drop-out rate of 56% predicts enrollment of 20 subjects per cleared indication (five) to reflect the underlying subject population adequately. As a result, an enrollment target of 100 subjects in total will be aspired.

